8.2. Efficacy Evaluation

8.2.1. Statistical Methods

Subjects will be stratified by Baseline vIGA-AD score and by study site, however due to a very low number of subjects in many sites, the analysis model will only stratify by vIGA-AD score stratum.

The primary endpoint will be tested using ITT population.

The primary estimand is described by the following attributes:

Treatment: Roflumilast cream 0.05%

Population: Subjects aged 2-5 years with Atopic Dermatitis

Endpoint: vIGA-AD success at Week 4

Handling of Intercurrent Events: A hybrid strategy will be used for handling intercurrent events. For events other than discontinuation due to AE or lack of efficacy (LoE), the occurrence of the intercurrent event will be considered irrelevant in defining the treatment effect of interest, i.e., the value for the variable of interest is used regardless of whether the intercurrent event occurs. This is the treatment policy strategy. Discontinuation due to an AE or LoE is considered to be informative about the subject's outcome and is incorporated into the definition of the variable. To that end, subjects who discontinue due to LoE or AE will be treated as non-responders for an analysis visit if the study day of the subject's last dose day falls within or prior to the relevant analysis visit window. Analysis visit windows will be defined in the SAP. This is a composite variable strategy.

Population-level Summary: The ratio of the odds of achieving vIGA-AD success after 4 weeks of using roflumilast cream 0.05%, relative to the odds of success after 4 weeks using a matching vehicle cream in the ITT population.

Missing data will be handled with multiple imputation methods (MI). A Cochran-Mantel-Haenszel (CMH) test stratified by the baseline vIGA-AD score used for randomization, will be performed separately for each of the multiply imputed analysis data sets, and results will be combined into one multiple imputation inference. The CMH test will not be stratified by study site as the 650 subjects will be randomized by over 90 sites leading to a low subject to site ratio. The common Mantel-Haenszel (MH) odds ratio and common MH proportion difference, adjusted for baseline vIGA-AD score used for randomization, will be provided along with their associated 97.5% and 95% CIs. Statistical significance will be concluded at the 2.5% significance level (2-sided).

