5.4 Windowing Conventions

Visits will be analysed as scheduled. Unscheduled, early termination visits, and/or retest measurements will only be included if a scheduled measurement is not available and the early termination or unscheduled/retest measurement falls within the analysis visit windows as described in [Table 2](#), [Table 3](#), and [Table 4](#) when appropriate. Unscheduled/retest measurements will be listed.

If there is more than one assessment for a given timepoint and analysis visit when a scheduled measurement is not available, the assessment closest to the target day will be considered.

Table 2 Analysis Visit Windows for Efficacy Endpoints, Vital Signs and Local Tolerability Assessment

Analysis Visit	Target Day	Lower Limit	Upper Limit
Week 1	8	2	11
Week 2	15	12	22
Week 4	29	23	43

Table 3 Analysis Visit Windows for Clinical Laboratory and Physical Examination

Analysis Visit	Target Day	Lower Limit	Upper Limit
Week 4	29	23	43

Table 4 Windows for the derivation of Average Weekly WI-NRS

Days for calculation of weekly average	Week (Derived)
(-6, 1) *	Baseline
(2, 8)	Week 1
(9, 15)	Week 2
(16, 22)	Week 3
(23, 29)	Week 4

* If Day 1 WI-NRS score is collected prior to or concurrently with the application of the first study drug (randomization for randomized subjects who were never treated with study drug), then the Day 1 WI-NRS score will be included in baseline calculation.

Note: With the caveat described in footnote **, if more than one WI-NRS score is available on the same day, the worst score of the day will be considered in the analyses.

 Innovaderm Research ■■■	STATISTICAL ANALYSIS PLAN, Version 1.0
Protocol Number: ARQ-151-315	Sponsor: Arcutis Biotherapeutics, Inc.

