5.5 Derived Variables

All questionnaire scores will be derived by Biostatistics in the ADaM datasets using the formulas defined below, even if calculated scores are present in the EDC database. All pre-calculated scores will be ignored for analysis.

- With the following exception, vIGA-AD Success = vIGA-AD of ‘Clear’ (0) or ‘Almost Clear’ (1) plus at least a 2-grade improvement from Baseline. The exception is that for subjects who discontinued early from study due to an AE or lack of efficacy, the subject will be considered as not having a vIGA-AD success (for MI and non-responder imputation analyses) or missing (for observed case analyses) for all pre-specified analysis visits (refer to Section 5.4) for which the subject’s last dose day falls within analysis visit window or is prior to the start of the analysis visit window.
- Average weekly WI-NRS = Average weekly WI-NRS pruritus score will be calculated as the sum of the daily WI-NRS scores reported during a specific week (in a 7-day period; refer to Section 5.4) of the study divided by the number of days with non-missing scores for that week. A minimum of 4 days of observations are needed to calculate an average weekly WI-NRS pruritus score. Otherwise, the corresponding average weekly WI-NRS pruritus score will be considered missing.
- With the following exception, a WI-NRS success = achievement of a 4- point reduction in average weekly WI-NRS pruritus score compared to average weekly WI-NRS baseline, calculated only for the subjects with average weekly WI-NRS score of ≥ 4 at baseline. The exception is that for subjects who discontinued early from study due to an AE or lack of efficacy, the subject will be considered as not having a WI-NRS success (for MI and non-responder imputation analyses) or missing (for observed case analyses) for all pre-specified analysis visits (refer to Section 5.4) for which the subject’s last dose day falls within the analysis visit window or is prior to the start of the analysis visit window.
- EASI total score = $0.2 (E_h + I_h + Ex_h + L_h) A_h + 0.2 (E_u + I_u + Ex_u + L_u) A_u + 0.3 (E_t + I_t + Ex_t + L_t) A_t + 0.3 (E_l + I_l + Ex_l + L_l) A_l$

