6.2.1 Multiple Imputation

All subjects, regardless of completion status, will have available data assigned to the pre-specified analysis visit using the analysis windows defined in Section 5.4, including the last available data of subjects who prematurely withdraws from the study. To comply with the definition of the primary estimand (Section 12.1.1), for subjects who discontinue due to lack of efficacy or adverse event, efficacy data assigned to a pre-specified analysis visit will be removed from the source data used for the multiple imputation process if subject's last dose day falls within the analysis visit window or is prior to the start of the analysis visit window used to assign data to a pre-specified analysis visit. This procedure will ensure that the data collected on or after these specific intercurrent events are not used in the imputation process.

For the primary efficacy endpoint of vIGA-AD success at Week 4 and the secondary endpoint of vIGA-AD success at Week 4 among subjects with a 'Moderate' randomized vIGA-AD score, the primary analysis will impute missing values using a Predictive Mean Matching (PMM) sequential-regression multiple imputation model for the ITT population. This is a three-step process.

1. The first step is to understand the pattern of missingness. In order to perform the multiple imputation, a monotone missing pattern has to be achieved. For example, if there exist values for baseline and Week 4 visits, but missing values for the Week 1 or 2 visits, the Markov-Chain Monte-Carlo (MCMC) method will be used to impute the small amount of missing data that may be missing at the intermediate visits that is required to make the missing data pattern monotone before applying the multiple imputation algorithm. This method uses a non-informative Jeffreys prior to derive the posterior mode from the expectation-maximization (EM) algorithm as the starting values for the MCMC method. The MCMC method will use the seed 6457149. The vIGA-AD score will be treated as a continuous variable for this step and the model will include the vIGA-AD scores at baseline, Week 1, Week 2, and Week 4. To avoid values that could not be observed in practice, imputed values will be rounded to the nearest integer (Round=1 option in PROC MI) in the range of 0 to 4.

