6.2.3 Tipping Point Analysis

As a sensitivity analysis to the multiple imputation analysis as described in Section 6.2.1 for the vIGA-AD success primary endpoint, a tipping point analysis will be performed in order to determine the inflection point at which the inference under the missing not at random (MNAR) assumption changes substantially.

The sensitivity analysis for the primary endpoint will be performed by using a specified sequence of shift parameters. The range of shift parameters to be included in this analysis are 0 to 2 by 0.2 for active and -2 to 0 by 0.2 for Vehicle. The values at which the results of the primary analysis are shifted from significant (i.e., $\alpha \leq 0.025$) to non-significant (i.e., $\alpha > 0.025$) will be determined.

Steps 1 and 3 of the analysis will be the same as for the multiple imputation analysis as described in Section 6.2.1. However, Step 2 of the analysis is where the shift parameters will be applied.

Imputed values for subjects who discontinue due to lack of efficacy or adverse event will be handled as described in Step 2 of Section 6.2.1 to ensure that these subjects are analyzed as non-responders at all visits on or after discontinuation of treatment.

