100%, where a subject's palm represents 1% of his/her total BSA). Secondly, the AD severity is evaluated based on 6 items (erythema, edema/papulation, oozing/crusts, excoriation, lichenification, and dryness) graded using a 4-point scale (half steps are not allowed): 0 (absence), 1 (mild), 2 (moderate), and 3 (severe). Lastly, 2 subjective items (loss of sleep and intensity of pruritus) are evaluated by having the subject indicates on a 10.0 cm visual analog scale (VAS) the point corresponding to the average value over the last 3 days (0 cm = none to 10 cm= maximum).

- The POEM is a tool used for monitoring atopic eczema severity. It focus on the illness as experience by the subject. It consists of a 5-point scale measuring the frequency of each of 7 AD symptoms (i.e., dryness, itching, flaking, cracking, sleep loss, bleeding, and weeping) over the past week scored from 0 (no days), 1 (1 to 2 days), 2 (3 to 4 days), 3 (5 to 6 days), and 4 (every day).

For subjects who discontinue due to lack of efficacy or adverse event, efficacy data assigned to a pre-specified analysis visit will be removed from observed data if subject's last dose day falls within the analysis visit window or is prior to the start of the analysis visit window used to assign data to a pre-specified analysis visit. This will be true for all endpoints described above.

For the continuous exploratory efficacy endpoints of change and percent change from baseline in average weekly WI-NRS, EASI total score, % BSA, CDLQI/IDQoL score (+ severity of dermatitis), DFI score, SCORAD score, and POEM score at Week 1, Week 2, Week 3 (WI-NRS only), and Week 4, descriptive statistics for the score, change from baseline and percent change from baseline will be presented by visit and treatment group based on observed data in the ITT population. For the continuous other efficacy endpoint of daily WI-NRS, descriptive statistics will also be presented similarly on a daily basis. Additionally, a plot of the mean (and standard error) daily WI-NRS scores over time for each treatment group will also be provided based on observed data. A similar plot will be provided for the percent change from baseline in daily WI-NRS.

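### The AE/lack-of-efficacy failure rule tests the last dose day against the analysis window and ignores the assessment date, so scheduled Week 1 and Week 2 scores taken before the last dose can be voided

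*SAP*

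**What the plan says.** **The rule.** SAP 5.5 covers children who discontinue for an adverse event (AE) or lack of efficacy. Their vIGA-AD Success, WI-NRS success and EASI responses count as not achieved in the multiple-imputation and non-responder analyses, "or missing (for observed case analyses) for all pre-specified analysis visits" where the "last dose day falls within analysis visit window or is prior to the start of the analysis visit window". SAP 6.2.2 and 12.1.1 apply the same test. Protocol 8.2.1 also makes the child a non-responder if the "last dose day falls within or prior to the relevant analysis visit window".

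**The data removal.** Under the same test, SAP 6.2.1 states that "efficacy data assigned to a pre-specified analysis visit will be removed from the source data used for the multiple imputation process", and SAP 12.3 states for the exploratory endpoints that "efficacy data assigned to a pre-specified analysis visit will be removed from observed data".

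**The stated purpose.** SAP 6.2.1 explains: "This procedure will ensure that the data collected on or after these specific intercurrent events are not used in the imputation process". SAP 6.2.3 gives a similar aim, that "these subjects are analyzed as non-responders at all visits on or after discontinuation of treatment".

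**The windows.** SAP 5.4, Table 2: Week 1 is Days 2-11 (target 8), Week 2 is Days 12-22 (target 15), Week 4 is Days 23-43 (target 29). The section opens "Visits will be analysed as scheduled"; an early-termination or unscheduled score is used only when the scheduled one is absent.

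**The order of events at a visit.** Protocol 7.2.1 has vIGA-AD scored before the cream is applied in the clinic. Footnote j of the visit schedule (Protocol Section 2) gives no study dose at Day 29/ET.

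**The concern.** The Week 1 and Week 2 windows extend 3 and 7 days past their target days. The rule asks only where the last dose lies relative to the window. A child scored on schedule while on treatment, who goes on dosing and stops later in the same window, therefore loses that score. It becomes a failure, is set to missing, or leaves the imputation source. With a last dose one day beyond the window edge, the same score stands.

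Four of the seven alpha-controlled secondary endpoints are at stake: vIGA-AD Success and clear/almost clear at Week 2, then the same two at Week 1. For these, a recorded value can be replaced because of a stop that came after the measurement, and whether that happens depends on a window edge. The planned sensitivity analyses do not show the effect for vIGA-AD Success or the EASI responses, because the non-responder and observed-case analyses carry the same rule.

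**Working it through.** **The plan's own figure.** No document quantifies this rule. The nearest stated figure is power above 90% for the Week 4 primary endpoint, which is not in dispute. With 217 and 433 children, 22% and 37%, and two-sided alpha 0.025:

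- pooled rate = (217 × 0.22 + 433 × 0.37)/650 = 0.320
- SE under the null = 0.0388; SE under the alternative = 0.0365
- power = Φ[(0.15 − 2.241 × 0.0388)/0.0365] = 0.958, so the statement holds

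**Step 1: which last-dose days void a scheduled score.** Let the visit be on day v and the window end on day U. The score precedes the last dose but is voided for last-dose days v+1 to U, which is U − v days. Counting a last dose on the visit day itself gives U − v + 1.

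| Visit | v | U | Strictly later last dose | Same day included |
|---|---|---|---|---|
| Week 1, on time | 8 | 11 | Days 9-11: 3 | Days 8-11: 4 |
| Week 2, on time | 15 | 22 | Days 16-22: 7 | Days 15-22: 8 |
| Week 1, 3 days early / late | 5 / 11 | 11 | 6 / 0 | 7 / 1 |
| Week 2, 3 days early / late | 12 / 18 | 22 | 10 / 4 | 11 / 5 |

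Example: scored on Day 15, last dose on Day 20. Day 20 lies in Days 12-22, so Week 2 is voided although the score was taken 5 days before the last dose. With a last dose on Day 23, the same score counts.

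**Step 2: Week 4.** No dose is given at Day 29/ET, so a scheduled Week 4 score normally follows the last dose. Such a child fails Week 4 under a window test or a date test. The only spillover is that the child's voided early scores no longer inform the imputation of other children.

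**Step 3: size.** Assumptions: visits on target, last-dose days spread evenly over Days 1-28, and 2-5% of the 650 children stopping for AE or lack of efficacy. The documents give no such rate.

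- Share of last-dose days affected: (3 + 7)/28 = 36%, or (4 + 8)/28 = 43% with same-day doses.
- Number stopping: 650 × 0.02 = 13; 650 × 0.05 = 32.5.
- Week 1: 13 × 3/28 = 1.4 to 32.5 × 4/28 = 4.6 children.
- Week 2: 13 × 7/28 = 3.3 to 32.5 × 8/28 = 9.3 children.
- Ceiling on the fall in the Week 2 rate at 5%, if every affected child were a responder: 5% × 7/28 = 1.25 points, or 5% × 8/28 = 1.43 points. At 2% it is 0.50 to 0.57 points.

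**Step 4: rule against purpose.** SAP 6.2.1 aims to drop data from the event onward, and SAP 6.2.3 speaks of visits from treatment discontinuation onward. If the last dose day marks the event, as the rule itself does, a Day 15 score with a last dose on Day 20 is neither. The rule removes more than its stated purpose requires.

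**The case against.** The strongest defence is that the rule is deliberate. It appears consistently in the protocol and throughout the SAP, and Protocol 8.2.1 calls it a composite variable strategy: stopping for AE or lack of efficacy is part of the outcome. On that view a child who stops during the Week 2 interval is a Week 2 non-responder by definition, and rewording the purpose sentences in SAP 6.2.1 and 6.2.3 would remove the conflict. That explains failure from discontinuation onward. It does not explain overwriting an earlier scheduled score, and rewording alone would leave the result dependent on the window edge.

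Three limits do stand:

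- A reader might infer that the lost scores precede the AE or the lack of efficacy. The documents show only that they precede the last dose; the problem that led to stopping may have begun while dosing continued.
- A reader might take 43% as the share of these children affected. It falls to 36% without same-day doses, which the on-or-after wording arguably covers. Both figures depend on visit timing and on even spread. Stops decided at a visit, with the last dose the day before, fail under either rule.
- An affected visit is not necessarily a changed result. A child who stops for lack of efficacy is unlikely to have been a responder, and forced failure then agrees with the score.

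**Conclusion.** The rule is wrong as written for Weeks 1 and 2. It voids scheduled on-treatment scores taken before the last dose and goes beyond the purpose the SAP gives for it. The change is worth making because it is cheap, although the effect is small: under the stated assumptions, about 1-5 children at Week 1 and 3-9 at Week 2. The ceiling of about 1.3-1.4 points at Week 2 applies at a 5% stopping rate with every affected child a responder; it is not an expected bias.

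The documents do not support stronger readings. The primary endpoint is not materially affected, and the first three secondary endpoints are also at Week 4. The affected endpoints are the last four in the hierarchy and early exploratory ones. The direction is unknown, since it depends on which arm has more such stops, and no change in any test conclusion has been shown. Nor does the SAP depart from the protocol here: both state the same window test.

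**What to change.** For Weeks 1 and 2, in SAP 5.5, 6.2.1, 6.2.2, 12.1.1 and 12.3:

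- Keep a scheduled assessment made on or before the last dose date as observed. Same-day scores are kept because vIGA-AD is scored before the clinic dose. State this explicitly, since the purpose sentences in 6.2.1 and 6.2.3 speak of data or visits on the event day as well as after it, and align those sentences.
- Treat the child as a non-responder if the assessment was made after the last dose date, or if there is no such assessment and the last dose falls within or before the window.

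Leave the Week 4 rule unchanged. Record the difference from Protocol 8.2.1 in SAP 3.5, which now reports no changes; SAP Section 1 provides for the SAP to govern where such changes are described.

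The cost is one date comparison in programming, using dates already collected, and a documented departure from the protocol wording. If the sponsor prefers to amend Protocol 8.2.1 itself, Protocol 9.6 requires sponsor and investigator agreement and IRB approval.

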5.6 Descriptive Statistics

All continuous variables will be summarized by presenting the number of subjects, mean, standard deviation (SD), median, Q1, Q3, minimum, and maximum.

Categorical variables will be presented as frequencies and percentages.

 Innovaderm Research ■■■	STATISTICAL ANALYSIS PLAN, Version 1.0
Protocol Number: ARQ-151-315	Sponsor: Arcutis Biotherapeutics, Inc.

Summary tables will be presented by visit, when applicable.

Change from baseline will be calculated as:

Assessment value at postbaseline visit X – baseline value.

Percent change from baseline will be calculated as:

$(\text{Assessment value at postbaseline visit X} - \text{baseline value}) \times 100\% / (\text{baseline value})$

Percent change from baseline will be missing in situation where baseline value equals to 0.

5.7 Statistical Tests

Unless otherwise specified, all statistical tests will be two-sided and will be performed with a significant level of 0.025. Confidence intervals (CIs) will be two-sided with both 97.5% and 95% coverage.

5.8 Handling of Retests, Unscheduled Visits, and Early Termination Data

Retests measurements, Unscheduled measurements, and ET visit assessments will be included in analysis and be summarized via analysis visit windowing according to the windowing conventions in section 5.4.

All data from retest, unscheduled measurements and ET visit assessments will be listed.

5.9 Software Version

All analyses will be performed using SAS® software Version 9.4 or higher.

6 STATISTICAL CONSIDERATIONS

6.1 Adjustments for Covariates

The covariate for this study is baseline vIGA-AD (vIGA-AD=2 - Mild vs. vIGA-AD=3 - Moderate at randomization). The CMH test will not be stratified by study site as the 650 subjects will be randomized by over 90 sites leading to a low subject to site ratio. Subgroup analyses will be generated for the baseline covariates.

